10.5.3.5 Supportive analyses for secondary objectives

Not applicable.

[figure not shown]
10.5.3.6 Tolerability

Tolerability of each study treatment will be assessed by summarizing the number of subjects with dose interruptions and dose reductions. Reasons for dose interruptions and dose reductions will be listed by subject and summarized.

10.5.4 Secondary PK objectives

The PK objective is to characterize the PK of asciminib in CML population.

Using PAS, summary statistics (n, mean, SD, coefficient of variation (CV) for mean, geometric mean, CV for geometric mean, median, minimum and maximum) will be presented for plasma concentration at each scheduled time point. The geometric mean with mean (SD) and individual plasma concentration versus time profiles of asciminib will be displayed graphically.

Using Safety set, concentration data will be listed. Concentration values below the limit of quantification (BLQ) will be set to zero by the Bioanalyst and displayed in listings as zero with a flag. BLQ values will be handled as zero in any calculations of summary statistics, but handled as missing for the calculation of the geometric means and CVs.

Pharmacokinetic parameters will be determined by non-compartmental method(s) using the pharmacokinetic profile of asciminib in patients with full PK sampling. PK parameters listed in [Table 10-1](#) will be derived and reported, when feasible.

Population PK modeling may be performed and the results may be reported in a separate population PK report. Data from this study may be combined with data from other studies for this analysis.

Table 10-1 Non compartmental pharmacokinetic parameters in full PK group

AUC0-12h	The area under the plasma concentration-time curve from time zero to 12 h (mass x time x volume-1) ^a
Cmax	The maximum (peak) observed plasma drug concentration after dose administration (mass x volume-1)
Tmax	The time to reach maximum (peak) plasma drug concentration after dose administration (time)
CL/F	The total body clearance of drug from the plasma after oral administration (volume x time-1)

[figure not shown]
10.6 Exploratory objectives

10.6.1 Exploratory efficacy objectives

- To evaluate the influence of factors such as major cytogenetic status at baseline, failure/intolerance to prior TKIs, line of therapy, gender, race and age on the effect of asciminib with respect to the primary efficacy endpoint.
- To characterize mutations in the BCR-ABL1 gene at Week 1 Day 1, upon confirmed loss of molecular response and/or at end of treatment and examine their association with molecular and cytogenetic response for asciminib vs. bosutinib.
- To assess the efficacy of asciminib when administered as treatment after bosutinib failure according to the 2013 ELN Guidelines.

10.6.1.1 Data analysis of exploratory efficacy objectives

Subgroup analyses will be performed to evaluate the influence of factors such as baseline major cytogenetic response status, baseline/Week 1 Day 1 BCR-ABL1 ATP-binding site mutation status (from local historical record and from Sanger Sequencing), failure/intolerance to prior TKIs, line of therapy, gender, race and age on the primary efficacy endpoint. In addition, a logistic regression analysis will incorporate the key baseline variables into the model to further evaluate the impact of these variables on the primary endpoint and to provide a treatment effect estimate which is adjusted for imbalances in the treatment groups. An adjusted odds ratio for the treatment effect with associated 95% confidence intervals will be presented. Mantel-Haenszel estimates of the common odds ratio and the corresponding 95% confidence interval will also be provided. The effect of asciminib when administered as treatment after bosutinib failure will be assessed using the Switch Analysis Set to estimate response rates (cytogenetic and molecular response) at all scheduled time points after switch, as well as time-to and duration

of response. The analysis of time-to-event endpoints will be conducted only if at least 5 events are observed.

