To assess clonal evolution during treatment with asciminib vs. bosutinib	Low level BCR-ABL1 mutation profiles assessed by mass spectrometry at Week 1 Day 1, upon confirmed loss of MMR and/or at EOT. Clonal evolution of several genes implicated in CML assessed by Next Generation Sequencing (NGS) methods	
[REDACTED]	[REDACTED]	
To compare the impact of treatment on patient reported outcomes (PRO) including CML-specific symptoms, patient quality of life, and impact on work productivity and activity impairment from baseline and EOT between treatment arms in all patients	Change in symptom burden and interference from baseline over time according to the MDASI-CML PRO instrument Change in patient's impression of CML symptoms according to Patient Global Impression of Change (PGIC) Change in health utility from baseline over time according to EQ-5D-5L Change in work productivity and activity impairment over time according to WPAI	
To compare the impact of treatment on health care resource utilization between treatment arms in all patients	Health care resource burden over time	
To assess the efficacy of asciminib when administered as treatment after bosutinib failure according to the 2013 ELN Guidelines	
 • Cytogenetic response rate (Complete, Partial, Major, Minor, Minimal, no response) at and by all scheduled data collection time points • MMR rate at and by all scheduled data collection time points 	Refer to Section 10.6

Objective	Endpoint	Analysis
	
• Time to MMR• Duration of MMR• Time to CCyR• Duration of CCyR• Time to treatment failure	

4 Study design

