- At any time after the initiation of therapy, loss of CHR, CCyR or PCyR.
- At any time after the initiation of therapy, detection of new BCR-ABL1 mutations which potentially cause resistance to study treatment (asciminib or bosutinib).
- At any time after the initiation of therapy, confirmed loss of MMR in 2 consecutive tests.
- At any time after the initiation of therapy, new clonal chromosome abnormalities in Ph+ cells: CCA/Ph+.

Conditions preventing patients to switch to asciminib

- Any Grade 3 or 4 toxicity which has not resolved to Grade 2 or lower within 28 days and before starting asciminib treatment.
- Asymptomatic (Grade 2) pancreatitis if not resolved within 28 days
- Disease progression while on bosutinib treatment. The following events are considered disease progression:
 - Accelerated phase (AP) as defined by any of the following:
 - $\geq 15\%$ blasts in the peripheral blood or bone marrow aspirate, but $< 30\%$ blasts in both the peripheral blood and bone marrow aspirate.
 - $\geq 30\%$ blasts plus promyelocytes in peripheral blood or bone marrow aspirate.
 - $\geq 20\%$ basophils in the peripheral blood.
 - Thrombocytopenia ($< 100 \times 10^9/L$) that is unrelated to therapy.
 - Blast crisis (BC) as defined by any of the following:
 - $\geq 30\%$ blasts in peripheral blood or bone marrow aspirate
 - Appearance of extramedullary involvement other than hepatosplenomegaly proven by biopsy (i.e. chloroma).
- QTcF at time of switch > 480 msec or inability to determine QTc interval

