10.1.6 Other analysis set

For duration of MMR and time to MMR, the MMR Responder Set that will be used is a subset of FAS and includes patients who achieve MMR at any time.

For CCyR rates at and by scheduled time points, the CCyR Analysis Set that will be used is a subset of FAS and includes patients who are not in CCyR at baseline.

For duration of CCyR and time to CCyR, the Cytogenetic Responder Set that will be used is a subset of FAS and includes patients who do not have CCyR at baseline and achieve CCyR at any time on study treatment.

Patients who will receive at least one dose of asciminib after bosutinib failure will form the Switch Analysis Set which will be used for safety and exploratory efficacy endpoints defined on these patients.

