The cumulative incidence of MMR will be graphically displayed by an increasing step function. This curve will increase each time (after randomization) at which a new responder is observed and thus will increase up to the best observed response rate (e.g. up to 50% if half of the patients in the analysis population are able to achieve response).

Time to MMR is defined in [Section 7.2.1.1](#) and calculated as: date of first MMR - date of randomization +1, for patients in the Molecular Responder Set. Descriptive statistics (minimum, maximum, median, quartiles, mean, sd) of time to MMR will be provided for the two treatment groups separately.

Cytogenetic Response

Patients in FAS will be categorized with counts and percentages provided for cytogenetic response (Complete, Partial, Major, Minor, Minimal, No Response) at and by (i.e. best response up to a specified time point) scheduled time points. Shift tables will also be employed to examine the changes in cytogenetic response category from baseline.

Since there are expected to be only limited numbers who are actually in CCyR at baseline the analysis of CCyR rate at and by scheduled time points will only include patients who are not in CCyR at baseline, i.e. the CCyR Analysis Set.

CCyR rates at and by scheduled time points etc. and the associated 95% confidence intervals based on the Pearson-Clopper method will be presented by treatment group with the analysis of these endpoints only including patients who are not in CCyR at baseline.

Confidence intervals for the differences in any response rates between treatment groups will be provided using the Wald method.

Statistical testing will be performed via CMH chi-square tests stratified by the randomization strata. The Mantel-Haenszel estimate of the common risk difference and the corresponding 95% confidence interval will also be provided.

Time to CCyR is defined for patients in the Cytogenetic Responder Set as: date of first CCyR - date of randomization +1. Descriptive statistics (minimum, maximum, median, quartiles, mean, sd) of time to CCyR will be provided for the two treatment groups separately.

The cumulative incidence of CCyR will also be graphically displayed by an increasing step function. This curve will increase each time (after randomization) at which a new responder is observed and thus will increase up to the best observed response rate.

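### Post-switch CCyR rate, time to CCyR and duration of CCyR are estimated on all switched patients, without excluding or separating those already in CCyR at switch

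*Combined protocol and SAP*

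**What the plan says.** Section 10.6.1.1 states that the post-bosutinib effect of asciminib "will be assessed using the Switch Analysis Set to estimate response rates (cytogenetic and molecular response) at all scheduled time points after switch", and adds time to and duration of response. Time-to-event endpoints are analysed only if at least 5 events occur.

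Section 10.1.6 gives the population: "Patients who will receive at least one dose of asciminib after bosutinib failure will form the Switch Analysis Set". It sets no condition on response status at switch.

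Table 3-1 (Section 3) lists the post-switch endpoints. They include "Cytogenetic response rate (Complete, Partial, Major, Minor, Minimal, no response) at and by all scheduled data collection time points", time to CCyR and duration of CCyR.

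For the randomised comparison, Section 10.5.2 says that the CCyR rate analysis "will only include patients who are not in CCyR at baseline, i.e. the CCyR Analysis Set". Under Section 10.1.6, time to and duration of CCyR use patients who "do not have CCyR at baseline and achieve CCyR at any time on study treatment". Section 10.5.2 also gives an unrestricted summary of cytogenetic categories on the FAS, with shift tables from baseline.

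Section 7.1.2.2 requires at least one failure criterion for the switch. One is "At any time after the initiation of therapy, confirmed loss of MMR in 2 consecutive tests". Another is a new BCR-ABL1 mutation that may confer resistance. Loss of CCyR is listed as a criterion of its own.

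**The concern.** Bosutinib failure as defined for the switch does not imply that CCyR has been lost. A patient with 0% Ph+ metaphases at the bosutinib end-of-treatment marrow may qualify on a molecular criterion alone. If the next marrow again shows 0% Ph+, the rule as written counts a CCyR after switch, although the response was reached on bosutinib.

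There is no control arm after the switch, so the estimated rate is itself the result. A carried-over CCyR raises that rate. It also has no meaningful time to response on asciminib, and its duration has no natural start on asciminib. It could also count towards the 5-event threshold. The plan guards against this in its randomised CCyR analyses but does not carry the safeguard into the switch phase.

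**Working it through.** **No plan figure to reproduce.** The documents give no expected number of switchers and no post-switch response rate. The sample size of 222 in Section 10.8 concerns the primary endpoint and does not enter here.

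**Step 1: can a patient switch while in CCyR?**
- Loss of MMR (Section 7.2.1.1) means BCR-ABL1 above 0.1% IS with at least a 5-fold rise from the lowest on-treatment value, confirmed in a later sample. Loss of CCyR is not required. It appears only among the events that waive the confirmatory sample.
- For study entry, Section 5.2 requires one of the two loss-of-MMR tests to be at least 1% IS. The switch criterion in Section 7.1.2.2 has no such floor, so a switcher may be only slightly above 0.1%.
- The new-mutation criterion sets no cytogenetic condition.
- Most other criteria exclude CCyR or argue against it: more than 95%, 65% or 35% Ph+ metaphases, loss of CCyR or PCyR, new clonal abnormalities in Ph+ cells, or BCR-ABL1 above 10%.

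The clear routes are therefore confirmed loss of MMR and a new mutation.

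**Step 2: do the restricted CCyR sets apply after the switch?** They are defined by status at baseline. The protocol uses a separate term, S-Baseline, for the switch phase, and Section 10.6.1.1 names the Switch Analysis Set. Nothing in the text reviewed extends the restriction.

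**Step 3: size.** Let c be the share of switchers in CCyR at switch, m the share of those still in CCyR at the post-switch visit, and r the CCyR rate among the rest. Then:

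- rate on all switchers = c·m + (1 − c)·r
- rate on switchers not in CCyR at switch = r
- excess = c·m + (1 − c)·r − r = c·(m − r)

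All three inputs are assumptions. With r = 20%, the rate on all switchers is:

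| c | m = 80% | m = 100% |
|---|---|---|
| 0% | 20% | 20% |
| 5% | 0.04 + 0.19 = 23% | 0.05 + 0.19 = 24% |
| 10% | 0.08 + 0.18 = 26% | 0.10 + 0.18 = 28% |
| 20% | 0.16 + 0.16 = 32% | 0.20 + 0.16 = 36% |

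Over c = 5–20%, m = 80–100% and r = 10–30%, the smallest excess is 0.05 × (0.80 − 0.30) = 2.5 points and the largest is 0.20 × (1.00 − 0.10) = 18 points. The excess is upward whenever m exceeds r, and zero when c = 0.

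**Step 4: are the data available?** Section 7.2.1.2 schedules a marrow aspirate at end of treatment, so cytogenetic status before the first asciminib dose should be on file.

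**The case against.** The strongest case on the other side is that the affected group may be very small or empty. Loss of MMR requires first reaching MMR on bosutinib. The plan assumes MMR rates of 15% at 24 weeks and 30% at 96 weeks, about 11 and 22 of 74 patients, and only those who then have a confirmed 5-fold rise would switch by this route. For mutations, Section 7.2.1.1 provides 12-weekly Sanger testing only for patients positive at Week 1 Day 1. Others are tested on confirmed loss of MMR or at end of treatment. This stands: it limits c, though it does not make c zero.

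A second argument is that the plan does not restrict everything in the randomised arms either. The FAS category summary keeps patients in CCyR at baseline, and the categorical post-switch endpoint in Table 3-1 resembles it. This also stands, and supports keeping the full set for that summary. It does not cover CCyR rate, time to CCyR and duration of CCyR, which the plan restricts in the randomised comparison.

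Third, a CCyR kept after switching may partly reflect asciminib. Post-switch marrows are scheduled from S-Week 24, up to 42 days may pass between bosutinib end of treatment and the first asciminib dose, and the Amendment 3 rationale says that disease burden will not improve without further treatment. A reader might infer that every such CCyR is owed to bosutinib alone. The documents do not support that, and it is why these patients should be shown separately rather than dropped.

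Finally, only part of the full document was available, so a derivation rule elsewhere could close the gap. Nothing in the text reviewed does.

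**Conclusion.** The gap in the definitions is real. As written, Sections 10.1.6 and 10.6.1.1 allow a CCyR present at switch to be counted as a post-switch response, contrary to the plan's own practice in its randomised CCyR analyses. The excess is about c(m − r): roughly 2.5 to 18 percentage points over the assumed ranges, and zero if nobody switches in CCyR.

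A reader might go further and infer that asciminib is in fact credited with responses it did not produce, or that such a report is nearly certain. With 25 switchers of whom 10% are in CCyR, the chance that at least one is in CCyR at switch is 1 − 0.9^25 = 93%. The documents do not support this inference. Neither input appears in them, no passage shows that any such patient exists, and equating that chance with a reported post-switch CCyR assumes that the response persists to the first scheduled post-switch marrow.

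The analysis is exploratory and untested. Post-switch efficacy data are kept out of the primary and secondary endpoints, so the primary and key secondary results, alpha and power are unaffected. This is a minor correction, worth making because it is cheap and the estimate has no control.

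**What to change.** In Section 10.1.6, define a subset of the Switch Analysis Set: switched patients not in CCyR at the last cytogenetic assessment before the first asciminib dose (the bosutinib end-of-treatment marrow). In Section 10.6.1.1, use this subset for post-switch CCyR rate, time to CCyR and duration of CCyR. Report patients already in CCyR at switch separately as maintained or lost.

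Keep the full Switch Analysis Set for safety and for the cytogenetic category summary, and add a shift table from switch baseline.

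For MMR, flag separately the few patients who may still be in MMR at switch through the new-mutation route. Those who switch for loss of MMR are not in MMR by definition. A separate MMR analysis set is optional; the plan has none for the randomised arms.

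The cost is a few sentences and a slightly smaller denominator in an exploratory analysis. No new assessments are needed.

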7.2 Assessment types

7.2.1 Efficacy assessments

7.2.1.1 Molecular response

Molecular response (MR) will be assessed in all patients randomized to each treatment arm as well as in patients that switch study treatment from bosutinib to asciminib.

Levels of BCR-ABL1 transcripts will be determined by real-time quantitative PCR (RQ-PCR) testing of peripheral blood and analyzed at a central testing laboratory. Log reduction in BCR-ABL1 transcripts levels from the standardized baseline value, or the percent ratio of BCR-ABL1 transcripts versus control gene (ABL) transcripts converted to a reference standard, international scale ([Hughes and Branford 2006](#)), will be calculated for each sample.

Major molecular response and related variables are defined as the following:

- Rate of Major Molecular Response (MMR) where MMR is defined as a ≥ 3.0 log reduction in BCR-ABL1 transcripts compared to the standardized baseline equivalent to ≤ 0.1 % BCR-ABL1/ABL % by international scale as measured by RQ-PCR, confirmed by duplicate analysis of the same sample
- Time to MMR defined as the time from the date of randomization to the date of the first documented MMR,
- Duration of MMR defined as the time from the date of first documented MMR to the earliest date of loss of MMR, progression to AP or BC, or CML-related death.

Loss of MMR is defined as increase of BCR-ABL1/ABL to > 0.1% by international scale (IS) in association with a ≥ 5 -fold rise in BCR-ABL1 from the lowest value achieved on study treatment and replicated by a second analysis of the same sample. Loss of MMR must be confirmed by subsequent sample analysis within 4 to 6 weeks showing loss of MMR associated with a ≥ 5 -fold rise in BCR-ABL1 from the lowest value achieved on study treatment, unless it is associated with confirmed loss of CHR or loss of CCyR or progression to AP/BC or CML-related death. Mutational analysis will be performed at a Novartis designated laboratory by Sanger sequencing at Week 1 Day 1, upon confirmed loss of MMR and/or at end of treatment. If the result at Week 1 Day 1 is positive for a mutation, analysis will be performed every 12 weeks.

The blood samples will be taken as described in [Table 7-1](#), [Table 7-2](#) and [Table 7-3](#).

Table 7-3 Blood samples (efficacy primary endpoint)

Sample Type	Volume	Visit	Time point
Blood for BCR-ABL1 quantification by RQ-PCR	20 mL	Screening/Baseline / S-Screening/S-Baseline*	Pre-dose
	20 mL	Week 4 / S-Week 4	Pre-dose

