10.5.2 Other secondary efficacy objectives

Unless otherwise stated the FAS will be used for the analysis of all other secondary efficacy endpoints. The exceptions are using the Molecular Responder Set for duration of MMR and time to MMR, the CCyR Analysis Set for CCyR rates, and the Cytogenetic Responder Set for duration of CCyR and time to CCyR.

No statistical testing of non-key secondary efficacy endpoints will be performed, and any analysis will be considered exploratory.

[figure not shown]
Molecular Response

MMR rates at scheduled time points (except 24 and 96 weeks which have been specified as primary and key secondary endpoints) will be evaluated in a similar fashion to the primary analysis of MMR rate at 24 weeks. Patients discontinuing the randomized treatment prior to a specific time point due to any reason will be considered as non-responders for that time point.

MMR rates by scheduled time points are defined as the proportion of patients who achieve MMR at or before the specified visit, i.e. if a patient achieves an MMR but then loses it before or at the visit, he/she will still be classed as achieving MMR by that time point.

For each endpoint the rate and the associated 95% confidence interval based on the Pearson-Clopper method will be presented by treatment group. Confidence intervals for the differences in any response rates between treatment groups will be provided using the Wald method.

Statistical testing will be performed via CMH chi-square tests stratified by the randomization strata. The Mantel-Haenszel estimate of the common risk difference and the corresponding 95% confidence interval will also be provided.

Duration of MMR is defined in [Section 7.2.1.1](#) as the time between the date of the first documented MMR and the earliest date of loss of MMR, progression to AP/BC, or CML-related death for patients in the Molecular Responder Set. The time will be censored at the last molecular assessment (PCR) date while on treatment for patients who have not experienced any of the above events.

Duration of MMR will be analyzed by K-M method and presented by K-M plots. The estimated rates of patients who are still responding at various time points will also be provided using K-M method.

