Duration of CCyR is defined as the time between date of first documented CCyR and the earliest date of loss of CCyR, progression to AP/BC, or CML-related death for patients in the

Cytogenetic Responder Set. The time will be censored at the last cytogenetic assessment date on treatment for patients for whom none of the above events is reported or last PCR evaluation on treatment indicating MMR.

Duration of CCyR response will be analyzed by K-M method and presented by K-M plots. The estimated rates of patients who are still responding at various time points will also be provided using K-M method.

Treatment failure, disease progression and survival

Time to treatment failure (TTF) is defined as the time from date of randomization to an event of treatment failure. The following events will constitute ‘treatment failure’, and are based on the ELN criteria ([Baccarani et al 2013](#)) defining failure of a second line treatment adapted to include discontinuation of randomized treatment as an event:

- No CHR or > 95% Ph+ metaphases at three months after randomization or thereafter
- BCR-ABL1 ratio > 10% IS and/or > 65% Ph+ metaphases at six months after randomization or thereafter
- BCR-ABL1 ratio > 10% IS and/or > 35% Ph+ metaphases at 12 months after randomization or thereafter
- Loss of CHR, CCyR or PCyR at any time after randomization
- Detection of new BCR-ABL1 mutations which potentially cause resistance to study treatment at any time after randomization
- Confirmed loss of MMR
- New clonal chromosome abnormalities in Ph+ cells: CCA/Ph+: at any time after randomization
- Discontinuation from randomized treatment for any reason

[figure not shown]
For patients who have not reached treatment failure, their TTFs will be censored at the time of last study assessment (PCR, cytogenetic, hematologic or extramedullary) before the cut-off date.

Progression-Free-Survival (PFS) is defined as the time from the date of randomization to the earliest occurrence of documented disease progression to AP/BC or the date of death from any cause (including progressions and deaths observed during the survival follow-up period) before the cut-off date.

The time will be censored at the date of last study assessment (PCR, cytogenetic, hematologic or extramedullary) or last post-treatment follow-up for patients without event.

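### The 5-event condition makes reporting of post-switch duration of MMR and CCyR depend on how many responses are lost

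*Combined protocol and SAP*

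**What the plan says.** Table 3-1 has an exploratory objective for the switch patients: "To assess the efficacy of asciminib when administered as treatment after bosutinib failure according to the 2013 ELN Guidelines". Its endpoints are cytogenetic and MMR rates at and by all scheduled time points, time to and duration of MMR, time to and duration of CCyR, and time to treatment failure. Section 10.1.6 defines the population: "Patients who will receive at least one dose of asciminib after bosutinib failure will form the Switch Analysis Set".

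Section 10.6.1.1 describes the post-switch efficacy analysis as "using the Switch Analysis Set to estimate response rates (cytogenetic and molecular response) at all scheduled time points after switch, as well as time-to and"; the phrase ends by adding how long responses last. The sentence that follows is "The analysis of time-to-event endpoints will be conducted only if at least 5 events are observed". It does not name the switch patients. However, it comes directly after the sentence about them, and the other analyses in that section (subgroups, logistic regression, Mantel-Haenszel odds ratio) concern the binary primary endpoint. The section does not say what an event is for each endpoint, why the number is 5, or what is shown when fewer occur.

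The events are defined elsewhere. Section 7.2.1.1 measures duration of MMR from "first documented MMR to the earliest date of loss of MMR, progression to AP or BC, or CML-related death". Section 10.5.2 measures duration of CCyR to the "earliest date of loss of CCyR, progression to AP/BC, or CML-related death for patients in the"; here the set meant is the Cytogenetic Responder Set. On patients still in MMR, Section 10.5.2 says: "The time will be censored at the last molecular assessment (PCR) date while on treatment for patients who have not experienced any of the above"; that is, patients without an event. For the randomised comparison the same section says "Duration of MMR will be analyzed by K-M method and presented by K-M plots", and sets no minimum number of events.

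**The concern.** A minimum event count looks like an ordinary guard against over-reading sparse data. For a duration endpoint, though, the event is the failure of the response. Patients who keep their response are censored and add nothing to the count. High retention therefore keeps the analysis out of the report, and enough losses bring it in.

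At stake is the durability part of the post-switch objective. If no duration analysis appears, a reader of the duration output alone cannot tell well-kept responses from too few responders. If it does appear in a small set, it has been selected for having many losses. The protocol applies no such condition to the same endpoints in the larger randomised groups.

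**Working it through.** **Inputs from the documents.** Threshold: 5 events (10.6.1.1). Events for duration: loss of response, progression to AP/BC, CML-related death (7.2.1.1, 10.5.2). Continuing responders: censored (10.5.2). Planned bosutinib arm, which bounds the number of switchers: 74 (10.8).

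**The plan's own figure.** The threshold of 5 has no stated derivation to reproduce. The bound of 74 does reproduce. With rates of 15% and 35%, 2:1 allocation, two-sided 5% and 90% power, the pooled rate is (0.15 + 2 × 0.35)/3 = 0.2833, and

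n = [1.960 × √(1.5 × 0.2833 × 0.7167) + 1.282 × √(0.15 × 0.85 + 0.35 × 0.65/2)]² / 0.20² = 73.2.

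Rounded up this is 74, and 3 × 74 = 222, as stated in 10.8.

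**Ceiling on reportable retention.** This step needs no assumption about loss rates. With R responders and at least 5 events, at most R - 5 are still in response, so the highest observed retention that can appear is (R - 5)/R = 1 - 5/R:

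- R = 5: 0%
- R = 10: 50%
- R = 14: 64%
- R = 20: 75%
- R = 26: 81%

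For R below 5 the condition cannot be met.

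**Chance that the analysis is run.** The documents give no number of switchers, no post-switch response rate and no loss rate, so all three are assumed. Taking 15 to 74 switchers and a response rate of 15% to 35%, R runs from 15 × 0.15 ≈ 2 to 74 × 0.35 ≈ 26. Let q be each responder's probability of an observed duration event by the cut-off. Then P(run) = P(X ≥ 5) with X ~ Binomial(R, q). For R = 10 and q = 0.15:

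1 - (0.197 + 0.347 + 0.276 + 0.130 + 0.040) ≈ 0.010.

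| R | q = 10% | 15% | 20% | 30% | 50% |
|---|---|---|---|---|---|
| 5 | 0% | 0% | 0% | 0.2% | 3% |
| 10 | 0.2% | 1% | 3% | 15% | 62% |
| 14 | 0.9% | 5% | 13% | 42% | 91% |
| 20 | 4% | 17% | 37% | 76% | 99% |
| 26 | 11% | 35% | 62% | 93% | 100% |

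**What is seen when the condition is met.** The expected observed loss proportion, given at least 5 events, is the sum over x ≥ 5 of (x/R) × P(X = x), divided by P(X ≥ 5). With a true loss of 10% it is 51% for R = 10 and 27% for R = 20.

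**The case against.** The strongest reply is that the condition covers only time-to-event analyses. Response rates at all scheduled time points after the switch carry no minimum, and Table 3-1 lists rates both at and by each visit. Under the definition in 10.5.2, a by-visit MMR rate still counts a patient who has since lost MMR, while an at-visit rate counts only patients in MMR at that visit. The gap between the two says something about durability. This stands, and it rules out two stronger readings:

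- A reader might infer that the post-switch objective goes unanswered. It does not, because most of the listed response endpoints are reported regardless.
- A reader might infer that, for time to response, the same condition hides poor efficacy. Fewer than 5 responders would show at once in the response rates.

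Visit rates are not a full substitute, however. Under 4.1.1 patients may switch until 96 weeks after the last randomisation, and under 4.3 treatment may end 48 weeks after the last switch. Follow-up is therefore staggered, and durability needs an estimate that handles censoring.

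Other points against also hold in part. The rule is fixed in advance and leaves no discretion. It is also unmet with fewer than 5 responders, or with 4 losses among 10, so a missing analysis does not prove durability. One responder count is used above for MMR and CCyR, which have different responder sets. Time to treatment failure is affected in the same direction, but its event list is wider and every switch patient is at risk, so 5 events are easier to reach. Finally, the pages available are part 2 of 3; text elsewhere could define the events or provide a listing.

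**Conclusion.** The point holds for duration of MMR and duration of CCyR: as written, whether the post-switch duration analysis is reported depends on its outcome. The ceiling of 1 - 5/R follows from the rule and the event definitions alone. The probabilities rest on assumed responder counts and loss rates, and on treating responders as independent with a common event probability by the cut-off.

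A reader might go further and infer that good durability would almost never be reported. That fits small responder counts: at 15% loss the chance is 1% for R = 10 and about 5% for R = 14. It does not hold over the whole assumed range, since the chance is about 35% for R = 26, and the documents do not say where R will fall.

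The consequence is limited. These are exploratory endpoints in an uncontrolled subset. No primary or key secondary test, alpha or sample size is affected. The change is still worth making, because it is cheap and removes outcome-dependent reporting of a listed endpoint.

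**What to change.** In 10.6.1.1, remove the event-count condition for post-switch duration of MMR and duration of CCyR. Report the Kaplan-Meier estimate as in 10.5.2, with numbers at risk, events, censorings and a confidence interval. When there are fewer than 5 responders, list individual durations with censoring status. Report time to treatment failure on the Switch Analysis Set whatever the event count. Leave time to response as defined in 10.5.2, descriptive in responders; extending it to all switch patients would change the endpoint.

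The cost is one changed sentence and two small extra outputs. Intervals will be wide and should be shown as such. No new data are needed.
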